#### **FOLLOWUP PLAN**

1. Case Communication to Clinical RN
2. Case Communication to Ostomy RN
3. Call Clinical RN
4. Call Ostomy RN
5. Consider Call Clinical RN
6. Evaluate trend of ostomy output
7. Stool thickening initiation Metamucil powder 1 tsp bid
8. Stool thickening escalation Imodium 2mg bid w/ meals (20 mins before meals)
9. Stool thickening escalation Imodium 2mg qid w/ meals (20 mins before meals)
10. Stool thickening escalation Imodium 4mg qid w/ meals (20 mins before meals)
11. Stool thickening escalation management by clinical team
12. IV fluids administration
13. Consider IV fluids administration
14. Consider Lab tests BMP, Mag, Phos
15. Consider Lab test CBC
16. Advance Diet as Tolerated (Clear liquids for 6 hours and then advance as tolerated to low residue diet)
17. Continue NPO status
18. Possible urgent clinic evaluation
- 19. Assess for home visit**

#### **LOGIC:**

- a) MCI, Afib w/ RVR, Tachycardia, Tachypnea (1, 3, 6)
- b) Other physiologic alert (5)
- c) Ostomy output >1200cc and patient on no stool thickening regimen (1, 5, 7, 13)
- d) Ostomy output >1200cc and patient on metamucil stool thickening regimen (1, 5, 13, 8)
- e) Ostomy output >1200cc and patient on imodium 2mg bid stool thickening regimen (1, 5, 13, 9)
- f) Ostomy output >1200cc and patient on imodium 2mg qid stool thickening regimen (1, 5, 13, 10)
- g) Ostomy output >1200cc and patient on imodium 4mg qid stool thickening regimen (1, 3, 13, 11)
- h) Ostomy output <500cc (1, 3)
- i) Has ANY Obstruction symptom, NEW, or WORSENING Obstructive Symptom, Patient not NPO (1, 3, 14)
- j) Has ANY Obstruction symptom, RESOLVED Obstructive Symptom, Patient not NPO (1)
- k) Has ANY Obstruction symptom, NEW or WORSENING Obstructive Symptoms, Patient NPO (1, 3, 14, 17)
- l) Has ANY Obstruction symptom, STABLE or IMPROVING Obstructive Symptoms, Patient NPO (17)
- m) Has ANY Obstruction symptom, RESOLVED Obstructive Symptoms, Patient NPO and Ostomy output 500-1200 (1, 3, 16)
- n) Has ANY Obstruction symptom, RESOLVED Obstructive Symptoms, Patient NPO and Ostomy output >1200, patient not on stool thickening regimen (1, 3, 16)

- o) Has the following Infectious symptoms (Redness at ostomy site, Drainage or swelling at ostomy site), NEW OR WORSENING Infectious Symptoms, Patient not on antibiotics (2, 4, 15)
- p) Has the following Infectious symptoms (Redness at ostomy site, Drainage or swelling at ostomy site), RESOLVED Infectious Symptoms, Patient not on antibiotics (2)
- q) Has the following Infectious symptoms (Redness at ostomy site, Drainage or swelling at ostomy site), NEW OR WORSENING Infectious Symptoms, Patient on antibiotics (2, 4, 15, 18)
- r) Has the following Infectious symptoms (Redness at ostomy site, Drainage or swelling at ostomy site), RESOLVED Infectious Symptoms, Patient on antibiotics (2)
- s) Has the following Infectious symptoms (Fever, Dysuria or Other), NEW, WORSENING, IMPROVING, OR STABLE Infectious Symptoms, Patient not on antibiotics (1, 3, 15)
- t) Has the following Infectious symptoms (Fever, Dysuria or Other), RESOLVED Infectious Symptoms, Patient not on antibiotics (1)
- u) Has the following Infectious symptoms (Fever, Dysuria or Other), NEW OR WORSENING Infectious Symptoms, Patient on antibiotics (1, 3, 15, 18)
- v) Has the following Infectious symptoms (Fever, Dysuria or Other), RESOLVED Infectious Symptoms, Patient on antibiotics (1)
- w) Has ANY Dehydration symptom, NEW, or WORSENING Dehydration Symptom, Patient not NPO (1, 3, 12, 14)
- x) Has ANY Dehydration symptom, STABLE OR IMPROVING Dehydration Symptom, Patient not NPO (1, 5, 13)
- y) Has ANY Dehydration symptom, RESOLVED Dehydration Symptom, Patient not NPO (1)

Table 5: CAPE Navigator or monitoring nurse alerts system for clinical team for Ileostomy

Table 5 will be configured into a note template within EPIC that allows for data elements to be captured and have all the logics built in to automatically highlight the recommended options for the monitoring nurse. The EHR smart note will be tested out by the research team to ensure the logic is correct.

If patients have any high risk alerts (MCI, Afib with RVR, Tachycardia, Tachypnea), the monitoring nurse will route a note and call clinical RN and evaluate the trend of ostomy output. All other physiological alerts will result in consideration call to clinical RN.

If patient ostomy output  $>1200\text{cc}$  and patient not on stool thickening regimen yet, the monitoring nurse will send note and call clinical RN, consider IV fluids administration and start stool thickening regimen escalation. Monitoring RNs will call clinical RNs for guidance on IV fluid administration guidance. The stool regimen escalation can occur daily while the output is  $\geq 1200\text{ml}$  in 24 hours. There is no monitoring nurse de-escalation protocol, and this will be performed by the clinical team. If a patient is non-adherent to Metamucil and/or Imodium and output is  $\geq 1200\text{ml}$  in 24 hours, medications will be maintained without escalation and patient will be counseled on the importance of adherence to medications. If the output continues to be greater than  $\geq 1200\text{ml}$  in 24 hours and there are no further options for escalation, the monitoring nurse will call the clinical care team for further guidance.

If ostomy output is  $<500\text{cc}$ , monitoring nurse will route note and call clinical RN. If patient has any new or worsening obstruction symptom but **not NPO** yet, monitoring nurse will route note and call clinical RN, and consider lab tests (BMP, Mag, Phos). If the obstructive symptoms resolve while patient is NPO, home health RNs will route note to clinical RN.

If patient has new or worsening obstruction symptoms but **is NPO already**, monitoring nurse will route note and call clinical RN, consider lab tests (BMP, Mag, Phos), and continue NPO status. If patient obstruction

symptom is stable or improving under the NPO status, monitoring nurse will keep patient NPO. If patient has resolved obstructive symptoms, still NPO and ostomy output is >1200 cc or between 500-1200 cc, monitoring nurse will note and call clinical RN, and instruct patients to advance diet as tolerated.

Any new or worsening redness at ostomy site, drainage or swelling at ostomy site, but **patient not on antibiotics**, monitoring nurse will note and call the ostomy RN for guidance in management, and consider CBC labs. If the above symptoms resolve without antibiotics, home health RN will call ostomy RN to update.

If patient has new or worsening redness at ostomy site, drainage or swelling at ostomy site, and is already on antibiotics, home health RNs will note and call ostomy RN, consider CBC labs and urgent clinic evaluation. If above symptoms resolve with antibiotics, home health RN will call ostomy RN.

Any new, worsening, improved or stable fever, dysuria or other infectious symptoms, but patient **not on antibiotics**, the monitoring nurse will note and call clinical RNs, and consider CBC labs. If the above symptoms resolve without antibiotics, the monitoring nurse will route note to clinical RN.

If patient has any new, worsening, improved or stable fever, dysuria or other infectious symptoms, **but is already on antibiotics**, the monitoring nurse will note and call clinical RNs, and consider CBC labs and urgent clinic visits. If the above symptoms resolve with antibiotics, the monitoring nurse will route note to clinical RN.

If patient has new or worsening dehydration symptoms, but not NPO, monitoring nurse will note and call clinical RN, consider IV fluids administration, and consider labs (BMP, Mag, Phos). If the dehydration symptoms are stable or improving while patient is not NPO, the home health nurses will route note to clinical RN, consider call clinical RN, and consider IV fluids administration under guidance of clinical team. When dehydration symptoms resolve, the home health RNs will route note to clinical RN.

We will be evaluating the high risk alerts and other physiological alerts to find the optimal alert types, thresholds and alerting frequency to maximize signal and minimize noise.

[figure not shown]

Figure 2: Process map for Ileostomy Patients

If care is escalated to the clinical care team which includes ostomy RNs, clinical RNs, and Physicians, the care team will pursue various interventions including counseling, altering medication therapy such as antibiotic therapy, procedures such as debridement or drainage, urgent visits to the colorectal surgery clinic ideally within 72 hours, and if no other available options readmission. These workflows will be left

to the discretion of the clinical care team given the nuance in taking care of these high-risk patients and the existing relationship and prior history with these providers. There are some standardized workflows that will be followed by the care team that are of note. Infusions of IV fluids will occur if the patient has  $\geq 1200$  ml of ileostomy output and dehydration symptoms. If these symptoms are identified, the goal will be to have monitoring nurse perform infusion at the patient's home. Also, all messaging from the monitoring nurses will be forwarded to the colorectal/ileostomy pool per protocol and logic in Table 5 to create the most rapid response back to the patient if required.

The final specs of the study will include:

1. Optimal inclusion/exclusion criteria.
2. Specific thresholds for high risk alerts for each use case
3. Specific thresholds for standard alerts (likely use physIQ standard thresholds)
4. Finalized physIQ alerts to CAPE navigators and monitoring nurse
5. Finalized CAPE navigator and monitoring nurse alerts to clinical care team
6. Finalized EPIC note
7. Finalized process maps
8. Finalized workflows by clinical care team
9. Discussion with physIQ to optimize the pinpointIQ portal to best support the CAPE navigators and monitoring nurse

The recruitment goals for this study is 10 ileostomy patients each for 30d of monitoring to evaluate if the remote monitoring technology from physIQ and cascading alert system and process can reduce 30-day readmissions. We will also perform economic calculations to determine if there is return on investment for this workflow tied to remote monitoring. Finally, we would like to do an in-depth analysis of the process to understand effectiveness, feasibility, efficiency, and bottlenecks. Some of the questions we would like to understand include: 1) What component of the cascading alert system provides the highest effectiveness of identifying patients at risk? 2) Can we reduce the number of monitored days and still effectively reduce 30 days of readmission? 3) Are there specific subgroups of patients who may benefit from the remote monitoring solution, or alternatively, are there subgroups who do not benefit from the remote monitoring solution? 4) Can we take our process maps and perform process simulation with data from the study and process mining to optimize our process and identify chokepoints with our current flow.

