Postoperative ileostomy patients are frequently readmitted because of physiologic perturbation and has readmission rates between 15-30% at NorthShore. Ileostomy patients are readmitted because of dehydration. There has been early work establishing the predictive potential of multivariate physiological telemetry (pinpointIQ) from a wearable sensor providing accurate early detection of impending rehospitalization for postoperative ileostomy with a predictive accuracy comparable to implanted devices. This population may benefit from remote continuous monitoring of vital signs tied to a cascading alert system to identify patients at risk of impending decompensation. There is limited literature looking at how continuous monitoring, ambulatory wearable devices can improve outcomes in high risk patients.

We propose conducting a mixed-methods study that will use a wearable device to collect ambulatory physiological data analyzed by a machine-learning algorithm to identify readmission risk. The alerts will be tied to a cascading escalation pathway that involves monitoring nurse, mid-level providers, specialists, and surgeons. We describe the quantitative and qualitative aspects of the study in detail below.

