## physIQ Alert System – Ileostomy

Patients:

Any positive symptom (dehydration, infection, or obstruction)
≥1200 ml ostomy output over one day
A high risk alert
A predefined number of standard alerts in a day

Table 4: PhysIQ alerts system for CAPE navigator or monitoring nurse for Ileostomy

For ileostomy the thresholds for the high-risk alerts and the number of standard alerts may be changed from patient to patient based on how each case progresses and the density and frequency of alerts. Determining the optimal thresholds for these two types of alerts will be a key aim of this study. The goal is again maximizing signal while minimizing noise.

If any of these conditions listed in Table 4 are met the monitoring nurse will call the patient and go through a predefined note with the following data elements and questions.

Infection Symptom
 
 
a) Fever
 
b) Dysuria
 
c) Redness at ostomy site
 
d) Drainage or swelling at ostomy site
 
e) Other (Free Text)
 

Obstruction Symptom
 
 
a) Nausea
 
b) Vomiting
 
c) Bloating
 
d) Decreased or no ostomy output
 
e) No gas through ostomy
 

Dehydration Symptom
 
 
a) Lightheadedness
 
b) Dry mouth
 
c) Low or dark urine output
 
d) Dizziness
 
e) Increased ostomy output
 

Symptom Change (Obstruction, Dehydration, Infection) [This can show up if any symptom is picked]
 
 
1. New
 
2. Worsening
 
3. Stable
 
4. Improving
 
5. Resolved
 

Ostomy output
 
 
a) 500-1200cc
 
b) >1200cc
 
c) <500cc
 

Is patient NPO? Yes/No

Is patient on antibiotics? Yes/No

Patient is on stool thickening regimen?
 
 
a) None
 
b) Metamucil powder 1 tsp bid
 
c) Imodium 2mg bid w/ meals (20 mins before meals)
 
d) Imodium 2mg qid w/ meals (20 mins before meals)
 
e) Imodium 4mg qid w/ meals (20 mins before meals)
 
f) Stool thickening managed by clinical team
 

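### Table 5, which drives the EPIC note, disagrees with Table 4 or the surrounding text on the 1200 ml cut-off and on rows c to f, w, x and u, and nothing says which version governs

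*Protocol*

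**What the plan says.** All of this is in protocol section 2.2.

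- **Trigger (Table 4).** Alerts include "≥1200 ml ostomy output over one day" and "Any positive symptom (dehydration, infection, or obstruction". The response is fixed: "If any of these conditions listed in Table 4 are met the monitoring nurse will call the patient".
- **Note fields.** Output is banded as below 500, 500 to 1200, and above 1200. The last of six stool-thickening options is "f) Stool thickening managed by clinical team".
- **Action list.** Action 3 is a call to the clinical RN, while action 5 is "5. Consider Call Clinical RN". Action 12 is "12. IV fluids administration", while action 13 only asks the nurse to consider it.
- **Table 5.** The first high-output row reads "c) Ostomy output >1200cc and patient on no stool thickening regimen (1, 5, 7, 13". Rows d, e and f also carry 5 and 13. Row g carries 3 and 13. Row w (new or worsening dehydration, not NPO) carries 1, 3, 12 and 14. Row x (stable or improving, not NPO) carries 1, 5 and 13.
- **Text after Table 5.** The logic goes into the EPIC note, which highlights the recommended options. The research team will test that the logic is correct. The paragraphs that follow then restate the rules in prose.
- **Care-team text after Figure 2.** Infusions occur when output is at least 1200 ml and dehydration symptoms are present. Messages are routed by the protocol and Table 5.

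**The concern.** The protocol gives the escalation rules twice, as coded rows and as prose, and the two differ. The nurse sees the coded version. Where they differ, the prompt is weaker or stronger than the prose, or absent.

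Most of the differences concern high output or dehydration. Section 1.2 says why that matters: "Ileostomy patients are readmitted because of dehydration". Aims 2, 3 and 5 also set out to finalise and evaluate these thresholds, workflows and processes. An evaluation of whether the pathway worked needs one known version of it. The planned test of the note does not supply this, because it names no reference: row c as coded is correct against Table 5 and incorrect against the prose.

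**Working it through.** No stated figure or formula is involved, so the check is a side-by-side reading followed by a count.

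**Four conflicts**

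| Point | Table 5 or note | Table 4 or text | Result |
|---|---|---|---|
| Cut-off | Rows c to g and the top note band need more than 1200 | Table 4, the daily-escalation and non-adherence rules and the infusion rule use 1200 or more; the prose sentence for row c uses more than 1200 | Exactly 1200 ml alerts but fires none of rows c to g |
| Row c | Action 5 (consider a call) | The nurse will call the clinical RN | Prompt weaker than text |
| Rows w and x | w: give fluids at any output; x: consider fluids at any output | Nurse text: consider in both; care-team text: infuse at 1200 ml or more with dehydration symptoms | w too strong below 1200; x weaker than the care-team rule at or above 1200 |
| Row u | New or worsening fever, dysuria or other, on antibiotics | Same action for stable or improved as well | Two states have text but no row |

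The text also has the nurse call the clinical RN for guidance on IV fluids, without limiting this to untreated patients. It therefore bears on rows d to f, which carry 5 and 13 as well.

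**Two omissions**

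- *Dehydration while NPO.* Rows w, x and y all require that the patient is not NPO. The nurse text for unresolved dehydration has the same limit. Take an NPO patient with stable obstruction, new dehydration, output of 500 to 1200 ml and nothing else recorded. Only row l fires, and it prompts only continued NPO.
- *Team-managed thickening.* Row g leads to this last regimen option, but no high-output row exists for it. Row h (below 500) still applies, whatever the regimen. The text's fallback, a call to the care team once escalation is exhausted, is not coded.

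**Count of unresolved symptom states**

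Four symptom groups (obstruction, ostomy-site infection, fever/dysuria/other, dehydration) × 4 unresolved change states × 2 NPO or antibiotic states = 32.

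- Row and text agree: i 2 + k 2 + l 2 + o 2 + q 2 + s 4 + u 2 = 16.
- Agreement depends on output: w 2 + x 2 = 4.
- Text but no row: fever/dysuria/other, stable or improving, on antibiotics = 2.
- No row and no nurse text: dehydration while NPO = 4.
- Silent in both, possibly intended as no action: ostomy-site stable or improving 4 + obstruction stable or improving and not NPO 2 = 6.
- Check: 16 + 4 + 2 + 4 + 6 = 32.

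Splitting the four w and x states by output gives 4 × 2 = 8 cases:

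- w below 1200 (2): stronger than either text. A new dry mouth at 600 ml prompts IV administration.
- w at or above 1200 (2): agrees with the care-team rule, though the nurse text says consider.
- x below 1200 (2): agrees with the nurse text.
- x at or above 1200 (2): weaker than the care-team rule.

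**High output by regimen.** Above 1200 ml, 5 of 6 regimen options have a row. At exactly 1200 ml, 0 of 6 do. Row w or x may still fire there if increased output is recorded as a dehydration symptom and the patient is not NPO.

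**The case against.** The strongest reply is that highlighted options are recommendations, that the note will be tested, and that finalising the alerts, note and workflows is itself an output of this 10-patient study. The nurse calls every alerting patient and can use judgement. This limits the harm, but it does not say which version is correct or what the test should compare the note with.

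Several narrower points stand:

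- Rows c to f all carry action 5, and only the last step, row g, carries a definite call. That pattern could be intended, with the prose loosely worded. Changing row c alone would prompt a firmer call for an untreated patient than for one still at high output on Imodium.
- The infusion rule says when infusions will occur. It does not say that they occur only then, and care-team workflows are left to clinical discretion. A reader might infer that fluids below 1200 ml are forbidden; the text does not say so. It only fails to support row w's unconditional prompt.
- The NPO gap is not a contradiction, since table and nurse text share the limit. The infusion rule has no NPO condition, so it would still reach NPO patients at 1200 ml or more.
- The cut-off conflict touches a single value, exactly 1200 ml.

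**Conclusion.** The conflicts on the cut-off, rows c to f, rows w and x, and row u are in the current text and should be resolved before the note is used. The NPO and team-managed-thickening gaps are lesser omissions.

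In size, 4 of 32 rule states depend on output and 2 have text but no row. Separately, all six regimen options lack a high-output row at exactly 1200 ml. These are rule states, not patients or alerts, and the protocol gives no frequency for any of them. No endpoint, estimate or sample size changes.

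Two stronger readings are tempting. One is that patients in these states go without care; the mandatory call to every alerting patient rules that out. The other is that the prose is right and Table 5 wrong; the protocol does not establish this, and for rows c to f the table may be what was meant.

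The conclusion assumes that the note will be coded as Table 5 is written, as the protocol says.

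**What to change.** Before the note is used:

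1. Use 1200 ml or more in rows c to g and n, in the note bands and throughout the text. Row m and the middle band then end below 1200.
2. In rows c to f, replace action 5 with 3. Alternatively, have the clinical team confirm the considered call for all four and correct the prose. Either way the ladder stays coherent.
3. In rows w and x, use action 13 below 1200 ml and 12 at or above it, under clinical-team guidance, and align the nurse text. Row w keeps its call to the clinical RN.
4. Make row u and its text cover the same change states.
5. Code the fallback call for 1200 ml or more on team-managed thickening.
6. Have the clinical team decide the dehydration rows for NPO patients.
7. State that the reconciled Table 5 is the reference against which the note is tested.

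The cost is one clinical sign-off, a wording amendment and a template edit, with no extra patients. The downside is some more calls to the clinical RN. If row u is extended or NPO rows are added, there will also be more prompts to consider a CBC, other labs, IV fluids or an urgent clinic visit. Section 4.7 makes participants responsible for office visits and diagnostic tests, so that choice should be deliberate.

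### Table 5 can highlight an oral thickening step and continued NPO for the same patient in 16 rule combinations, because rows c-f ignore NPO status and rows k-l ignore ostomy output

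*Protocol*

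**What the plan says.** All of this is in Protocol section 2.2.

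- **Output rows.** Rows c-f of the Table 5 logic apply when output exceeds 1200cc and differ only by current regimen. Row d reads "Ostomy output >1200cc and patient on metamucil stool thickening regimen (1, 5, 13, 8". The codes refer to the follow-up plan list. Code 7 starts Metamucil. Code 8 is "Stool thickening escalation Imodium 2mg bid w/ meals (20 mins before meals", and codes 9 and 10 are the same drug at higher doses, also timed to meals. None of the four rows mentions NPO.
- **Obstruction rows for NPO patients.** Row k reads "Has ANY Obstruction symptom, NEW or WORSENING Obstructive Symptoms, Patient NPO (1, 3, 14, 17" and row l reads "Has ANY Obstruction symptom, STABLE or IMPROVING Obstructive Symptoms, Patient NPO (17". Code 17 keeps the patient NPO. Neither row mentions output or regimen.
- **How the rows are used.** The text below Table 5 says the Epic template will have "all the logics built in to automatically highlight the recommended options for the monitoring nurse". It adds: "The EHR smart note will be tested out by the research team to ensure the logic is correct".
- **Calls.** Code 3 is a call to the clinical RN; code 5 is only to consider one. The text below Table 5 requires a call when output is high and no regimen has been started. It also says: "Monitoring RNs will call clinical RNs for guidance on IV fluid administration guidance".

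**The concern.** The two groups of rows look at different fields of the same note, so both can apply at once. Take an NPO patient on Metamucil with improving bloating and an output of 1300cc. Rows d and l both apply, and the note highlights Imodium with meals alongside keeping the patient NPO.

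This looks like an oversight. Every obstruction and dehydration row (i-n and w-y) carries an NPO condition; rows c-f do not. Row n covers an NPO patient with output above 1200cc, so the plan foresees that state.

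At stake is the advice shown to a nurse about a possibly obstructed patient. The finalised Epic note is also one of the listed study outputs, so an uncorrected conflict could be carried into it.

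**Working it through.** There is no stated figure to reproduce. The check applies rows c-n as printed to an NPO patient with at least one obstruction symptom and output above 1200cc, and collects every code that would be highlighted.

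**Inputs.** Rows c-f: (1, 5, 7, 13), (1, 5, 13, 8), (1, 5, 13, 9), (1, 5, 13, 10). Row k, new or worsening symptoms: (1, 3, 14, 17). Row l, stable or improving symptoms: (17).

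| Current regimen | Output row | Thickening code | Combinations with row k | Combinations with row l |
|---|---|---|---|---|
| None | c | 7 (Metamucil start) | 2 | 2 |
| Metamucil | d | 8 (Imodium, with meals) | 2 | 2 |
| Imodium 2mg bid | e | 9 (Imodium, with meals) | 2 | 2 |
| Imodium 2mg qid | f | 10 (Imodium, with meals) | 2 | 2 |
| Total | | | 8 | 8 |

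**Size of the conflict.**
- All combinations with a thickening code and code 17: 4 regimens x 4 symptom states = 16.
- Imodium steps timed to meals: 3 x 4 = 12.
- Metamucil starts: 1 x 4 = 4.
- Row g (Imodium 4mg qid) is not counted, because code 11 hands thickening to the clinical team. A regimen already managed by the clinical team triggers no output row.

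**Who is told.**
- All 16 carry code 1 (routed note) and code 13 (consider IV fluids), both from rows c-f.
- The 8 row-k combinations carry code 3, a required call.
- The 8 row-l combinations carry only code 5. For example, rows d and l together give 1, 5, 8, 13, 17.
- The text below Table 5 requires a call for patients not yet on a regimen. That covers 2 of the 8 (stable and improving), leaving 8 - 2 = 6.
- If the IV-fluid guidance sentence applies whenever fluids are to be considered (code 13), every state has a required call and 0 remain. If it applies only once fluids are intended, 6 remain. The range is therefore 0 to 6.

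**After the fix.** Suppressing codes 7-10 whenever code 17 is active leaves 0 conflicting combinations.

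**Neighbouring wording.**
- *Row n.* For symptoms that resolve while NPO with output above 1200cc, row n gives the call and diet advance (code 16) only with no regimen, so code 16 is absent for 5 of the 6 regimen entries. The text below Table 5 orders both without a regimen limit.
- *Row j.* One sentence in that text says resolution while NPO leads to a routed note only. It stands where row j falls in the sequence and gives row j's action, but row j is for patients who are not NPO.
- *Row c.* The row gives code 5, where the text requires a call.

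**The case against.** **NPO is not defined.** If it permits oral medicines, the 4 Metamucil starts are not clearly in conflict. This stands, and the claim is limited accordingly. The 12 Imodium steps remain, because they are tied to meals.

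**The text may already settle it.** Daily escalation is worded as permitted, whereas keeping the patient NPO is worded as an instruction. There is also a rule that holds medication without escalation for non-adherent patients. If NPO bars oral medicines, that rule might be stretched to the 12 combinations where a regimen is already in use. Both points soften the conflict. Neither is encoded in Table 5, and the non-adherence rule, with its counselling on adherence, fits a patient told to take nothing by mouth poorly.

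**There are safeguards.** The nurse has phoned the patient, the highlights are recommendations, a note is always routed, and the logic is to be tested and finalised during the study. All true. But a build faithful to Table 5 reproduces the conflict, and the protocol does not say that these combinations will be tested.

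**Stronger readings that the documents do not support.**
- *Eight states leave the conflict without clinician input.* The call sentences bring this to between 0 and 6, and a note is routed in all of them.
- *NPO patients with dehydration have no route to fluids, because rows w-y require the patient not to be NPO.* The care-team workflow says "Infusions of IV fluids will occur if the patient has" high output and dehydration symptoms, with no NPO condition.
- *Rows c-f should never apply to an NPO patient.* Code 17 is absent in the 4 resolved-symptom states and in patients without obstruction symptoms, so nothing conflicts there.
- *The plan holds competing policies for symptoms that resolve while NPO.* The position of the odd sentence suggests that a "not" was dropped.

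**Conclusion.** The concern holds and should be fixed. As printed, Table 5 highlights a thickening step together with continued NPO in 16 combinations. Twelve cannot be followed as written by a patient kept NPO; four are in conflict only if NPO bars oral medication. Between 0 and 6 of the 16 lack a required call, depending on how far the IV-fluid sentence reaches.

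The 16 are rule combinations, not expected patients. Some are less plausible than others, since two of the five obstruction symptoms (reduced or absent output, no gas) sit poorly with output above 1200cc. Nothing in the protocol gives their frequency among the 10 patients, and no harm is shown. The conclusion also rests on the visible text: Figure 2, the process map, is not shown and might state a precedence.

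**What to change.** **Main change.** State in Table 5 that codes 7-10 are not highlighted when code 17 is active. In the 16 combinations, highlight 1, 3, 13 and 17, plus 14 under row k, and leave thickening to the clinical RN on that call. Leave rows c-f unchanged for resolved symptoms and for patients without obstruction symptoms. Include the 16 combinations in the planned note test, and say whether NPO allows oral medication.

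**Cost.** One precedence rule in the note template and 16 test cases, with no extra data. By Table 5 alone, a required call replaces an optional one in 8 states. Adding a not-NPO condition to rows c-f and a call row for every NPO patient with high output would also clear the conflict. But it would remove thickening in the 4 resolved states and add required calls in 14 states, 6 of them without a conflict.

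**Secondary wording.** The clinical team should confirm that the routed-note sentence on resolution while NPO was meant for patients not NPO, matching row j. Drop the no-regimen limit from row n so that it agrees with the text. Make row c and the sentence requiring a call agree, in whichever direction the clinical team chooses.
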